In countries such as Singapore, Jordan, the United States, and Canada, the collaborative care model has been shown to optimize therapeutic outcomes of patients with DM as evidenced by improvements in surrogate markers such as HbA1c, BP, LDL and TG (Table 1).¹⁸⁻²¹ These studies had a follow-up period ranging from 3 to 9 months. Although the degree or level of improvements vary across countries, the collaborative care model has shown to improve clinical outcomes of patients with DM.

Author	Study	Country	Clinical Outcomes				Comments
(year)	Design		HbA1c	SBP	LDL	TG	
			(%)	(mm Hg)	(mmol/L)	(mmol/L)	
Siaw	Randomis	Singapore	INT: -	No	No	No	Treatment
MYL et	ed		0.3% at	significant	significant	significant	satisfaction and
al.	controlled		3-month	changes	changes	changes	distress were also
(2017) ¹⁸	trial		and -	over 6	over 6	over 6	assessed (better
			0.5% at	months	months	months	outcome in INT). INT
			6-month				also shown to
							significantly reduce
							direct medical costs
							as compared to UC.
Jarab AS	Randomiz	Jordan	INT: -	INT: -5.8;	INT: -0.6;	INT: -0.5;	Medication
et al.	ed		0.8; UC:	UC: +1.1	UC: No	UC: +0.2	adherence and self-
(2012) ¹⁹	controlled		+0.1		change		care techniques also
	trial						improved in INT.
Scott DM	Randomis	United	INT: -	INT: -3.4;	INT: -0.5;	NIL	Quality of life was
et al.	ed	States of	1.7; UC:	UC: +2.1	UC: -0.2		assessed using
$(206)^{20}$	controlled	America	-0.9				DQOL; some
	trial						components favour
							IN I but total scores
							were not significantly
							different between INI
	D. I. I.						
Katherine	Randomis	Canada	IN 1 : -	INT: -2.0;	IN1:-7.7;		DQLCLIQ and SF-36
$(2005)^{21}$	ea		0.29;	00: +7.0	UC: +1.6	+40.6;	Were assessed.
(2005)21	controlled					00:-0.9	
	unai		+0.72				such as global role
							impact health
							distross and social
							uisiress, and social
							significantly improved
							in INT
							IN INT.

Table [•]	1. Im	provements ir	Surrogate	Markers	from (Collaborative	Care Model
IUNIC			ounoguio	marker 5	in onit y	oonusorunve	

Abbreviations: INT, intervention; UC, usual care.

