The purpose of this study is to determine the effectiveness of the collaborative care model in Singapore in which clinical pharmacists, nurses and dietitians are active participants who collaborate with physicians in caring for patients with type 2 DM. Since type 2 DM is a cardiovascular risk equivalent, co-morbidities such as hypertension (HTN) and dyslipidaemia (DLP) will also be evaluated to assess the holistic care provided for our patients afflicted with these top chronic diseases in Singapore.

Specifically, this study aims to evaluate the long-term effectiveness and sustainability of an integrated collaborative care model comprising of a healthcare team (physician, clinical pharmacist, nurse, and/or dietitian) compared to the usual or conventional healthcare model (physician-centred care) mainly in the following outcomes (Table 2).

Types of Outcomes	Descriptions				
Clinical	• Glycated haemoglobin (HbA1c), systolic blood pressure (SBP), low density				
	lipoprotein (LDL), total cholesterol, high density lipoprotein (HDL) and fasting				
	triglyceride (TG) levels				
	 Incidence of minor and major hypoglycaemia 				
	 DM-related clinical visit and hospitalization 				
Humanistic	Health-related quality of life				
	Self-care management				
	Diabetes-related distress				
Economic	Cost effectiveness				
	Productivity				

Table 2. Outcome Measures for Proposed Study

The central hypothesis of this study is that patients with type 2 DM under the collaborative care model will have greater improvements in the clinical, humanistic and economic outcomes assessed than those under conventional care.

Data collection period:

12 March 2018 to 12 March 2020

Study Design and Methodology:

Study Design and Setting

This proposed project is a prospective, randomized controlled study to be conducted over a 12month period. This multi-centre study will be conducted in Bukit Batok and Choa Chu [name] Polyclinics.

Study Participants

Patients aged \geq 21 years with Type 2 DM (HbA1c > 7%) and polypharmacy (\geq 5 medications) will be eligible for this study. Patients with Type 1 DM or who are unable to communicate independently in English, Chinese or Malay will be excluded from this study.

Procedures

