The sum of the costs incurred will be compared between the two groups using the Wilcoxon rank-sum test as the cost data are not expected to be normally distributed. General linear models with a log-link to the gamma distribution will be used to conduct multivariate analysis of costs between the groups. Gamma distributions are well suited for cost data since it a right-

skewed distribution. A cost-effectiveness analysis will be performed in which the effectiveness is defined by reduction in HbA1c between baseline and the 12-month follow-up. The incremental cost-effectiveness ratio will be calculated in which the difference in total costs between two groups is divided by the difference in the reduction in HbA1c between the two groups. Sensitivity analysis will be conducted to evaluate the influence of uncertainties in the variables and assumptions employed on the analysis results.

Data Entry and Storage:

All research-related electronic data collected will be de-identified, coded and entered in Microsoft Excel spreadsheet that will be password-protected and will be stored together with research-related paper documents in the investigators office at the National University of Singapore Department of Pharmacy, Faculty of Science. All patient information will be kept strictly confidential, following the policies of the study institution(s) involved. For hardcopy data, they will be stored in designated locked cabinet(s) or room(s) that are accessible to authorized study personnel only. For electronic data, they will be stored on in a secured computer that is password-protected. The databases will not contain subject identifiers and the data linking subject identifiers and the subject identification codes will be stored separately. These documents will be retained for a minimum of three years after study completion or as per institutional policies.

Confidentiality of Data and patient Records:

Investigators in this study will have access to all research-related data on a need-to-know basis or as per institutional policies. Collaborators in this study will only have access to researchrelated data that has been coded and has no patient related identifier. Only the principal investigators and co-investigators or collaborators will have access to the data in the excel spreadsheet. There will not be any sharing or releasing of raw data to any other persons.

Publication:

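### The protocol names a point ICER as its only cost-effectiveness statistic, with no stated interval for the cost difference, although its cited evidence points to lower cost with better HbA1c, where the ratio's size is uninformative (minor)

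*Protocol*

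**What the plan says.** The economic analysis is described at the end of the protocol's Data Analysis section.

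- **Cost comparison.** "The sum of the costs incurred will be compared between the two groups using the Wilcoxon rank-sum test". For adjustment, "General linear models with a log-link to the gamma distribution will be used to conduct multivariate analysis of costs between the groups".
- **Effect measure.** For the cost-effectiveness analysis, "the effectiveness is defined by reduction in HbA1c between baseline and the 12-month follow-up".
- **Summary statistic.** "The incremental cost-effectiveness ratio will be calculated in which the difference in total costs between two groups is divided by the difference" in HbA1c reduction between the groups. No other cost-effectiveness statistic is named, and nothing is said about a negative ratio.
- **Uncertainty.** "Sensitivity analysis will be conducted to evaluate the influence of uncertainties in the variables and assumptions employed on the analysis results". Whether this is deterministic or probabilistic is not stated.

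Three other places bear on the expected direction. The central hypothesis, under Specific Aims and Objectives, is that patients under collaborative care "will have greater improvements in the clinical, humanistic and economic outcomes assessed than those under conventional care"; Table 2 lists the economic outcomes as cost effectiveness and productivity. The Table 1 row for the earlier Singapore trial reports a fall in HbA1c (0.3% at 3 months, 0.5% at 6 months) and a significant reduction in "direct medical costs" against usual care. The background text also states that collaborative care has lowered overall health care costs.

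**The concern.** A ratio of two differences is easy to read when both have the same sign: it is then a price per HbA1c point gained, or a saving per point given up. When the signs differ it is negative and its size says nothing useful. The cost evidence that the protocol cites points to such a case, lower cost with better HbA1c.

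The second difficulty is precision. The numerator is a difference in mean costs. The rank-sum test does not estimate that difference, and the coefficient of a log-link gamma model is a ratio of mean costs. So none of the named analyses, as described, gives an interval for the quantity that drives the economic result. A trial of this size could report a point ratio, or simply declare collaborative care dominant, on a cost difference that is well within chance.

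**Working it through.** **Evaluable numbers.** The section on the number of subjects gives a standardised effect of 0.4, two-sided alpha 0.05, 80% power and 20% dropout. The t-based calculation needs 99.08, rounded up to 100 per arm, and 100 / 0.8 = 125. The protocol's 125 per arm reproduces, and about 100 per arm remain evaluable.

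**Why the size of a negative ratio is uninformative.** Let dC be the cost difference and dE the difference in HbA1c reduction (collaborative minus usual care). The values are illustrative.

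| dC | dE | dC/dE |
|---|---|---|
| -200 | +0.4 | -500 |
| +200 | -0.4 | -500 |
| -400 | +0.4 | -1000 |
| -200 | +0.2 | -1000 |
| -200 | +0.8 | -250 |

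Rows 1 and 2 are opposite results with one value. From row 1, doubling the saving (row 3) moves the ratio to -1000, while doubling the HbA1c gain (row 5) moves it to -250. Two improvements push the number in opposite directions.

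**Sampling error.** The documents give no cost mean, cost SD or HbA1c SD, so each difference is expressed in SDs of its own variable. Assumptions: 100 per arm, normal and independent estimates. SE = sqrt(2/100) = 0.141, so a 95% interval has half-width 1.96 × 0.141 = 0.277 SD.

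- P(looks cheaper and better) = Φ(dE/SE) × Φ(-dC/SE)
- P(looks dearer and worse) = Φ(-dE/SE) × Φ(dC/SE)
- P(interval for the cost difference lies below zero) = Φ(-dC/SE - 1.96)

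With a true effect of 0.4 SD, which assumes that the planning effect applies to HbA1c:

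| True cost difference (SD) | Looks cheaper and better | Negative ratio | Cost interval below zero |
|---|---|---|---|
| -0.4 | 99.5% | 99.5% | 81% |
| -0.2 | 91.9% | 91.9% | 29% |
| -0.1 | 75.9% | 75.9% | 10% |
| 0 | 49.9% | 50.0% | 2.5% |
| +0.2 | 7.8% | 8.1% | <0.1% |

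Worked line: at dC = -0.2, Φ(2.83) × Φ(1.41) = 0.998 × 0.921 = 0.919, and Φ(1.41 - 1.96) = 0.29. A simulation of 1,000,000 draws agrees to within about 0.1 percentage point on the first two results.

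**Illustration in money.** Assume a cost SD of $1,500 to $3,000, an HbA1c-change SD of 1.5, a saving of $150 to $300 and a gain of 0.3 to 0.5 points. The same formulas give a negative ratio in 62% to 91% of trials. The result is dearer and worse in at most about 3%. The half-width of the cost interval is 0.277 × 1,500 = about $416, up to 0.277 × 3,000 = about $832, wider than either assumed saving. For a $150 saving (0.1 SD at $1,500) and a 0.3-point gain (0.2 SD), the central 95% of simulated ratios is -6.67 to +4.93 in SD units. Multiplied by 1,500 / 1.5 = 1,000, that is about -$6,670 to +$4,930 per HbA1c point.

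**The case against.** The ICER as written is the standard definition, and nothing else in the protocol contradicts it. Intervals, bootstrap details, acceptability curves and dominance rules commonly sit in an analysis plan that is not shown, so their absence alone is no error. That stands; the point is offered as a better method, not as a mistake in the text.

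Four stronger readings are tempting and are not supported:

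- *The result could not be interpreted.* The cost and HbA1c differences must be computed to form the ratio, and the protocol also compares both between groups. The quadrant would be visible. If the true effect is 0.4 SD, the effect estimate falls below zero in only about 0.2% of trials, so with a true saving a negative ratio would almost always mean cheaper and better.
- *The protocol hypothesises cheaper and better.* It hypothesises greater improvement in economic outcomes. A dearer but more effective programme with a positive ICER also fits. Lower cost is inferred from the cited background studies.
- *Uncertainty is ignored, or the sensitivity analysis is one-way.* A sensitivity analysis is planned and could be probabilistic. Its wording points to variables and assumptions, but it does not exclude sampling error.
- *The gamma model conflicts with the ICER.* The protocol does not say that the numerator comes from that model, so an adjusted cost ratio may stand beside an unadjusted cost difference.

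The percentages rest on assumed inputs, and about half negative at zero cost difference follows automatically. What the objection leaves standing is that the only named summary is a bare ratio, and that none of the named analyses is stated to give an interval for the mean cost difference.

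**Conclusion.** The point holds as a minor, inexpensive improvement. The protocol settles on a point ratio whose size has no useful order in the direction of its own cited cost evidence, and it names no analysis that puts an interval on the numerator. With about 100 evaluable patients per arm, a bare ratio or an unqualified claim of dominance would carry more certainty than the data support. At a true saving of 0.2 SD of cost and an effect of 0.4 SD, about 92% of trials would look dominant while about 29% could exclude a zero cost difference. With no true saving, half would look dominant. These figures assume normal, independent estimates and cost differences that the documents do not give. The analysis is one of many outcomes, and the sample size is unaffected.

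**What to change.** Replace the ICER sentence in the Data Analysis section with wording to this effect:

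> The difference in mean cost per patient and the difference in mean HbA1c reduction will each be reported with a 95% confidence interval. Intervals will come from a non-parametric bootstrap of patients within arm, keeping each patient's cost and effect paired (at least 2,000 draws). Incremental net benefit with its 95% interval will be reported over a stated range of values per HbA1c point. An ICER will be given only when the estimates lie in the north-east quadrant (dearer, better) or south-west quadrant (cheaper, worse). Otherwise dominance will be stated with its bootstrap probability.

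Keep the planned sensitivity analysis as an addition, and say whether it is deterministic or probabilistic.

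The cost is a change of wording and a little more analysis code, with no new data. The team must also choose the range of values per HbA1c point in advance. The downside is an economic conclusion that may look less certain than a single ratio would.
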